7.8 Criteria for Evaluability and Removal/Withdrawal from Treatment

Criteria for evaluability of the Trial

- Patients must have received a total of at least 80% of the intended dose of doxorubicin, ifosfamide, and pazopanib to be evaluable for the trial. If less than this amount is received, the patient may remain on the study, but will not be evaluated for primary endpoints.

Criteria for stopping therapy:

- Substantial non-compliance with the requirements of the study.
- Any adverse event which, in the Investigator's opinion, requires termination of the study medication.
- Disease progression, unless at the discretion of the Investigator (in collaboration with Novartis) continued treatment with study drug is appropriate.
- The patient would benefit from additional radiation therapy beyond that specified in the protocol.
- Request by the patient or a legal representative/relative to stop the treatment.
- The patient presents with a beta-HCG test consistent with pregnancy. Pregnancy will be reported along the same timelines as a serious adverse event.
- The patient uses illicit drugs or other substances that may, in the opinion of the Investigator, have a reasonable chance of contributing to toxicity or otherwise interfering with results.
- The development of a second malignancy that requires treatment, which would interfere with this study.
- The patient is lost to follow-up.
- Interruption in administration of pazopanib or chemotherapy for greater than 3-week delay.
- Development of an intercurrent illness or situation which would, in the judgment of the Investigator, affect assessments of clinical status and study endpoints to a significant degree.

Criteria for study withdrawal:

- Study closure.
- Patient decision to withdraw from both study therapy and follow-up.

The Investigator will make every reasonable effort to keep each patient in the study unless it is in the patient's best interest to discontinue participation. If a patient is removed from the study or declines further participation, all End of Treatment evaluations should be performed if the patient is willing and able to be assessed. A description of the reason(s) for withdrawal from the study will be recorded on the case report form (CRF). The Investigator should also ensure that all patients are followed up for survival and recurrence after the Final Visit.

Relevant visit data should be entered on the CRF and any unused study medication will be accounted for and returned for all patients participating in the study, even for a brief period of time. Patients who discontinue following entry will have relevant information completed and recorded on the CRF. All patients who discontinue because of adverse events or clinically significant laboratory abnormalities should be followed up until they recover or stabilize, and the subsequent outcome will be recorded. If any patient should die during the trial or within 30 days of stopping study treatment, the Investigator will inform the IRB and the Novartis representative. The cause of death should be recorded in detail, within 24 hours, on a serious adverse event (SAE) form and reported to the IRB and Novartis.

Subjects who are withdrawn from the study prior to surgery will be replaced and randomized to treatment with pazopanib versus placebo according to the 2:1 design.

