3.0 STUDY OBJECTIVES

3.1 Primary Objectives

- To determine the absolute values and changes in standardized uptake values (SUV) by FDG PET before and after a 14 day Run-in period of pazopanib versus placebo, and to compare this to the change in SUV following pre-operative chemotherapy.
- To evaluate the correlation between antiangiogenic activity and pazopanib drug exposure.
- To assess the response rate by RECIST criteria after the 14 day Run-in period of pazopanib versus placebo and compare this to the response rate following pre-operative chemotherapy.

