Baseline staging scans including a positron emission tomograph with a built-in CT component (FDG-PET), MRI of the primary tumor, and diagnostic CT chest are required at Screening (within approximately 14 days of the Run-in Period, Day 1). After the 14-day Run-in period of pazopanib versus placebo, and prior to commencement of preoperative chemotherapy, subjects will undergo repeat FDG-PET and MRI of the primary tumor. After 2 cycles of chemotherapy, FDG-PET and MRI of the primary tumor will be repeated.

CT of the chest without contrast will be performed approximately every 3 months for the first year following surgery and MRI (or CT) of the primary site of the tumor will be performed every 6 months.

ECOG Performance Status

The ECOG performance status will be assessed at Screening, Run-in Period Day 1 and Day 1 of each subsequent cycle, Final Visit, and at the 30-day Follow-up Visit. See **Appendix B** for ECOG criteria.

Pharmacokinetic Studies

Trough level (22-24 hrs after pazopanib dosing): A blood sample (4 mL K2EDTA purple top blood collection tube) will be drawn to assess the trough plasma pazopanib concentration during the 14 day Run-in period of pazopanib monotherapy, after completion of adjuvant chemotherapy, and every 3 months thereafter until completion of pazopanib maintenance therapy. During the Run-in period, the trough level will be drawn twice during Days 10 through 14: 1) one trough on any of Days 10-14 and 2) on the day of the FDG PET after the Run-in period, 22-24 hours after the patient's last dose of pazopanib versus placebo. After completion of surgery/adjuvant chemotherapy, the trough will be drawn once during each of the following periods: 1) Week 2 (Days 10-15 after restarting pazopanib), Weeks 3-4 after

restarting pazopanib, and then every 3 months for 1 year). If all trough levels are drawn, a total of 8 samples are possible in a single subject.

An optional full intensive pharmacokinetic visit will be performed in consenting patients during Weeks 2-4 in subjects following surgery/adjuvant chemotherapy. Blood (4 mL K2EDTA purple top blood collection tube) will be obtained at the following timepoints: immediately before pazopanib dosing (within 5 minutes before giving pazopanib on the day of PK dosing) and 1, 2, 3, 4, 6, 8 hour timepoints (+/- 10 minutes), and 24 hrs (range 22 to 24 hours) after dosing (a total of 8 samples/subject).

Biomarker Studies

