7.0 TREATMENT PLAN

TREATMENT	PAZOPANIB RUN-IN ^A	CYCLES 1 AND 2 ^B	CYCLES 3 AND 4 ^C	PRE- OP RT ^D	SURGERY ^E	CYCLES 5 AND 6 ^B	POST-OP RT ^F
DOXORUBICIN		75 MG/M2 CIVI OVER 3 DAYS, EACH CYCLE WEEKS 3-8	75 MG/M2 CIVI OVER 3 DAYS, EACH CYCLE WEEKS 9-14	WEEKS 16-21	2-4 WEEKS AFTER COMPLE- TION OF PRE- OPERATIVE THERAPY	75 MG/M2 CIVI OVER 3 DAYS, EACH CYCLE 2-4 WEEKS AFTER SURGERY	2-4 WEEKS AFTER COMPLETION OF CHEMO-THERAPY
IFOSFAMIDE		2 GM/M2 IV, DAYS 1-5, EACH CYCLE WEEKS 3-8 (6-DAY WASHOUT AFTER PAZOPAN -IB	2 GM/M2 IV, DAYS 1-5, EACH CYCLE WEEKS 9-14			2 GM/M2 IV, DAYS 1-5, EACH CYCLE 2-4 WEEKS AFTER SURGERY	

TREATMENT	PAZOPANIB RUN-IN A	CYCLES 1 AND 2B	CYCLES 3 AND 4C	PRE- OP RT D	SURGERY E	CYCLES AND 6B 5	POST-OP RTF
MESNA^I		AFTER EACH DOSE OF IFOS	AFTER EACH DOSE OF IFOS			AFTER EACH DOSE OF IFOS	
PAZOPANIB OR PLACEBO	800 MG PO DAILY, WEEKS 1-2						
PAZOPANIB MAINTEN- ANCE^G							1 WEEK AFTER COMPLETION OF CHEMO/RT (DURATION 52 WEEKS)

A Pazopanib versus placebo run-in 14 days

B Chemotherapy cycles every 21 days. Cycle 1 may not commence until a 6 day washout period of pazopanib has occurred.

C Cycles 3 and 4 will only be given if there is a response to chemotherapy identified on imaging after cycles 1 and 2.

D Pre-operative radiation administration, when given, will consist of external beam 50 Gy in 25 fractions of 2 Gy/fraction over 5 weeks. If the target volume encompasses sensitive structures such as bowel or lung, the dose can be reduced to 45 Gy in 25 fractions of 1.8 Gy without protocol violation.

E Surgery should be planned for 2-4 weeks after completion of pre-operative therapy. Any planned post surgical adjuvant chemotherapy should be initiated only after adequate wound healing has been achieved. Patients who require a delay of greater than 10 weeks from the initial surgery due to inadequate wound healing will be removed from further protocol therapy.

F Post-operative radiation administration, when given, will consist of external beam 50 Gy in 25 fractions of 2 Gy/fraction over 5 weeks, followed by 10 Gy boost (in 5 fractions) to a reduced, or boost, volume. For contaminated or close margins, the boost dose will be 10 - 16 Gy; for microscopically positive margins, 16 - 20 Gy, and for grossly positive margins, 20 – 26 Gy.

For patients who received pre-operative radiation, but have positive surgical margins, 16 – 20 Gy (2Gy x 8 - 10 fractions) will be given by external beam following any planned adjuvant chemotherapy.

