7.1.2 Chemotherapy Administration

Pre-operative chemotherapy will consist of doxorubicin and ifosfamide administered on an inpatient basis. Subjects may also receive 2 to 4 cycles of post-operative chemotherapy, (up to 6 cycles total of neoadjuvant plus adjuvant chemotherapy).

Doxorubicin: 75 mg/m² by continuous IV infusion days 1 through 3 of each cycle.

Ifosfamide: 2.0 g/m² over 4 hours IV, days 1 through 5 of each cycle.

Mesna: 400 mg/m² IV pre, 4 hours post, and 8 hours post each dose of ifosfamide.

Hydration: D5W with 100 meq/L sodium acetate, 20 meq/L potassium acetate, 4 meq/L magnesium sulfate continuous IV infusion at a rate of 83 mL/hour, begun approximately 2 hours prior to chemotherapy and discontinued after completion of chemotherapy and Mesna.

Cycle 1 of chemotherapy may only commence after a minimum 6-day washout period of pazopanib.

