11.0 ASSESSMENT OF EFFICACY

Evaluability: In order for a patient to be evaluable, 80% of the intended dose of all three drugs must be delivered in the first 2 cycles of chemotherapy.

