14.0 STATISTICAL CONSIDERATIONS

14.1 Analysis plan

The primary objective is to compare FDG SUV (SUV lean, SUL) measures for patients receiving pazopanib and placebo. The primary endpoint is the percent change in SUV between baseline and the end of the 14-day Run-in period of pazopanib or placebo. The comparison will likely be conducted using a two-sided Wilcoxon rank sum test, often used as a nonparametric alternative to the two-sample t-test for studies with a small sample size. Additional endpoints will include SUV percentage change between baseline and the end of preoperative therapy, absolute post-treatment SUV (at 14 days and following preoperative chemotherapy), and absolute difference in SUV.

The analysis sample for the primary pharmacodynamic analysis is expected to exclude patients who have incomplete data due to missed PET scans or due to study withdrawal for toxicity. However, reasons for missing data will be examined, and multiple imputation will be considered if patients with incomplete data would be considered as part of the target population for future development of pazopanib in sarcoma. However, insofar as sarcoma is heterogeneous, the sample size is small, and covariates are limited – multiple imputation may not be applicable.

These pharmacodynamic response measures will be compared to tumor response by RECIST criteria, using graphical displays. Continuous measures of pharmacodynamic response (percentage change in SUL; response assessed using MRI) will also be compared to the trough plasma pazopanib, using graphical displays and correlation coefficients to investigate dose-response relationships related to patients' differing metabolism of pazopanib.

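### The 80%-dose evaluability rule can drop a patient from the run-in SUV comparison for a chemotherapy shortfall that arises after that endpoint is measured, and Sections 7.8, 11.0 and 14.1 are not reconciled

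*Combined protocol and SAP*

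**What the plan says.** **The dose rule.** Section 7.8 makes evaluability depend on receiving at least 80% of the intended total of all three drugs, with no time window. The consequence of falling short is "If less than this amount is received, the patient may remain on the study, but will not be evaluated for primary endpoints". The opening of Section 11.0 states the rule differently: "80% of the intended dose of all three drugs must be delivered in the first 2 cycles of chemotherapy".

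**The endpoint.** Section 14.1: "The primary endpoint is the percent change in SUV between baseline and the end of the 14-day Run-in period of pazopanib or placebo". Section 3.1 also lists a run-in RECIST objective as primary: "To assess the response rate by RECIST criteria after the 14 day Run-in period of pazopanib versus placebo". Section 4.2.1 adds the correlation of pazopanib trough with SUV and MRI change.

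**The timing.** Section 4.3 places the second scans after the run-in, and "prior to commencement of preoperative chemotherapy, subjects will undergo repeat FDG-PET and MRI of the primary tumor". Section 7.1.2: "Cycle 1 of chemotherapy may only commence after a minimum 6-day washout period of pazopanib". In the Section 7.0 table the pre-operative pazopanib or placebo entry is "800 MG PO DAILY, WEEKS 1-2", so none is given during the chemotherapy cycles.

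**The analysis sample.** Section 14.1 expects the primary pharmacodynamic analysis to "exclude patients who have incomplete data due to missed PET scans or due to study withdrawal for toxicity". It sets no dose condition and refers to neither 7.8 nor 11.0.

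**Replacement.** Section 7.8 replaces subjects withdrawn before surgery. It says nothing about replacing those who stay on study below 80%.

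**The concern.** Whether a patient counts in a randomised comparison should not depend on something that happens after the outcome has been recorded. Here a patient can complete the blinded run-in with both PET scans and then leave the run-in comparison because doxorubicin or ifosfamide was later cut back. The same applies to run-in RECIST response and to the run-in trough correlations. Section 7.7.3 leaves chemotherapy dose modification to the investigator's discretion, so part of the selection is discretionary.

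The three sections can also give different answers for the same patient, which leaves the analysis set open to a choice made after the data are seen. With 21 patients planned and one powered comparison (Section 14.2), each complete observation matters. The plan also does not say whether the run-in scans of a patient who is later withdrawn and replaced stay in the analysis.

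**Working it through.** **1. Order of events.** Baseline PET; 14 days of pazopanib or placebo; second PET; washout of at least 6 days from the last dose before cycle 1; cycles 1 and 2; third PET. The run-in SUV change is fixed at the second PET. Every doxorubicin or ifosfamide shortfall comes later.

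**2. One patient under three rules.** Take a patient with both run-in PETs, full run-in dosing and full doxorubicin, who receives 7 ifosfamide days in cycles 1 and 2. Planned days: 5 × 2 = 10. Delivered: 7/10 = 70% (8/10 would be exactly 80%).

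- Section 11.0, two-cycle window: out.
- Section 14.1 read alone: in, because both scans exist.
- Section 7.8, no window: depends on later cycles. Two further full cycles give (7 + 10)/20 = 85%, which passes. If those are post-operative cycles, they follow unblinding (Section 6.0; Section 7.0, note G). What counts as the intended dose after a permitted reduction is not defined.

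Taken literally, 11.0 also asks for 80% of pazopanib in cycles when none is given. Neither section says how the pazopanib condition applies to placebo patients.

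**3. The plan's own power figure.** Section 14.2 inputs: difference 30 points, SD 20, n = 21 at 2:1 (14 and 7), power about 90%. Alpha is not stated; 0.05 two-sided is assumed.

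Power = Φ(30/SE − 1.96), with SE = 20 × √(1/m + 1/n).

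For 14:7, SE = 20 × √(1/14 + 1/7) = 9.26, and Φ(3.24 − 1.96) = 0.90. The stated figure is reproduced with all 21 patients analysed.

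**4. Illustrative losses.** Losses of 3 and 6 patients, not replaced, are assumptions chosen only to show scale.

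| Analysed | Lost | SE (points) | Normal | t-test | Exact Wilcoxon |
|---|---|---|---|---|---|
| 14:7 | 0 | 9.26 | 0.90 | 0.87 | about 0.83 |
| 12:6 | 3 | 10.00 | 0.85 | 0.80 | about 0.75 |
| 10:5 | 6 | 10.95 | 0.78 | 0.72 | about 0.64 |

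The t-test column uses the noncentral t distribution. The Wilcoxon column uses 400,000 simulated trials per row with normal data and exact critical values. The SE rises by 8% (10.00/9.26) and 18% (10.95/9.26). Part of the Wilcoxon fall is not lost information: the attained alpha of the exact test drops from 0.046 at 14:7 to 0.040 at 10:5. The difference between 0.90 and 0.83 in the first row reflects the choice of test, not the evaluability rule.

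**5. Carry-over into chemotherapy.** Section 2.4 gives a mean half-life of 30.9 h at 800 mg daily, and 52.3 h as the longest value listed. Six days is 144 h.

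- 144/30.9 = 4.66 half-lives; 2^(−4.66) is about 4% remaining.
- 144/52.3 = 2.75 half-lives; 2^(−2.75) is about 15% remaining.

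**The case against.** **Section 14.1 can be read as governing.** It is the specific statistical text, and a patient with both run-in PETs has complete data for that endpoint whatever follows. This is the best defence and would make the matter largely a missing cross-reference. It does not settle it: the sample is worded only as what is expected, and 7.8 names the primary endpoints explicitly and makes no exception for those already measured.

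**The chemotherapy condition has a purpose.** Sections 4.2.1 and 11.1 include SUV after two cycles among the primary measures, and there a chemotherapy-exposure condition makes sense. That stands. The fault is that the condition is not confined to those measures.

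**Some losses are made good.** Patients delayed more than 3 weeks come off study (7.7.3), and withdrawals before surgery are replaced. So 6 unreplaced losses looks extreme. Patients who stay on study below 80% are still not covered.

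**Bias between arms.** A reader might infer that pazopanib lowers chemotherapy tolerance, since Section 7.4.1 calls it a weak CYP3A4 and CYP2D6 inhibitor and Section 10.3 links doxorubicin to both enzymes, and so that the comparison is biased. The documents do not support that. The washout leaves only about 4% to 15% of the drug. Section 7.4.1 does advise caution for 14 days after the last dose, so some interaction cannot be excluded, but no arm difference in shortfall is documented. Blinding also limits deliberate selection, though only under 11.0's window; 7.8 without a window can reach cycles given after unblinding.

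**It is a pilot.** True, and the RECIST and trough analyses are graphical or correlational. The run-in SUV comparison is still a formal two-sided test with a power statement.

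**Conclusion.** The rule is wrong as written for the run-in endpoints. Section 7.8, and 11.0 if it supplies the window, allow complete randomised run-in data to be excluded for events after the outcome, and the plan does not say whether 14.1 overrides them. This follows from the text and needs no assumed loss rate.

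The demonstrable consequence is lost precision. On the assumptions above, 3 unreplaced losses cost about 5 points of power by the normal approximation (0.90 to 0.85), and 6 cost about 12 (0.90 to 0.78). The Wilcoxon falls are larger, partly through attained alpha. These figures are illustrations, not forecasts.

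Two stronger readings do not hold. It is tempting to say that the 7-of-10-day patient is excluded by both dose rules, but that is certain only under 11.0. It is also tempting to say that the result will be biased. That would need shortfall to differ by arm and to be related to SUV change; neither is shown, and size and direction cannot be estimated. An argument about bias between arms does not reach the trough correlations at all, since they concern pazopanib patients only.

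This should be fixed before analysis. Confidence is high on the inconsistency and low on any bias.

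**What to change.** Reconcile Sections 7.8, 11.0 and 14.1, with text to this effect:

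- **Headline run-in comparison** (SUV change, and likewise run-in RECIST response and MRI change): all randomised patients with both the baseline and the post-run-in assessment, analysed as randomised, whatever chemotherapy followed, including patients later withdrawn and replaced.
- **Sensitivity analysis:** the same comparison limited to patients who took at least 80% of their assigned run-in tablets, pazopanib or placebo.
- **Run-in trough correlations:** those of the headline patients who were randomised to pazopanib and have a run-in trough.
- **Post-cycle-2 SUV and RECIST endpoints:** apply the 80% doxorubicin and ifosfamide condition here only, counted over cycles 1 and 2. Report these endpoints for all patients with the post-cycle-2 assessment as well, so that the effect of the filter is visible.
- **Missing data:** keep 14.1's review of reasons, and its conditional multiple imputation for patients without a post-run-in scan.

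The cost is wording in three sections and a few extra summary analyses; no added scans or patients, and no change to treatment. The downside is small: patients with low run-in exposure may slightly dilute the headline effect, and the sensitivity analysis would show that.

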4.2 Endpoints

4.2.1 Primary Endpoints

- Absolute values and changes in standardized uptake values (SUV) of tumors measured by FDG-PET pre- and post receipt of pazopanib versus placebo, and post receipt of 2 cycles of preoperative chemotherapy
- Tumor response by RECIST criteria
- Correlation of pazopanib trough concentration with the change in SUV from FDG PET and change in RECIST measurements on MRIs

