7.7.3 Chemotherapy Dose Modifications

A treatment cycle may not begin unless the patient's absolute neutrophil count (ANC) is $\geq 1500/\mu\text{L}$ and platelet count is $\geq 100,000/\mu\text{L}$ (without transfusion).

Patients who experience Grade 3 or 4 hematologic or non-hematologic toxicity that is attributable to chemotherapy and not to the underlying disease should have chemotherapy held until the toxicity resolves to \leq Grade 1. Dose modifications for doxorubicin and ifosfamide-related toxicity will be based on the Investigator's discretion.

Patients who are delayed greater than 3 weeks due to non-resolution of such toxicity will be taken off study.

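### The 80% chemotherapy-dose rule in 7.8 and 11.0, applied as written, removes patients from a primary SUV comparison that is complete before chemotherapy starts, and it conflicts with 14.1

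*Combined protocol and SAP*

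**What the plan says.** - **Endpoint (14.1).** "The primary endpoint is the percent change in SUV between baseline and the end of the 14-day Run-in period of pazopanib or placebo".
- **Timing (4.3).** After the run-in, "prior to commencement of preoperative chemotherapy, subjects will undergo repeat FDG-PET and MRI of the primary tumor". Section 7.1.2 allows cycle 1 only after a pazopanib washout of at least 6 days.
- **Other primary endpoints (4.2.1).** These include SUV after two chemotherapy cycles, RECIST response, and "Correlation of pazopanib trough concentration with the change in SUV from FDG PET and change in RECIST measurements on MRIs". Section 4.3 schedules two run-in troughs, the later one on the day of the post-run-in PET.
- **Dose rule (7.8).** A patient must receive at least 80% of the intended dose of each of the three drugs. No time window is given. "If less than this amount is received, the patient may remain on the study, but will not be evaluated for primary endpoints".
- **Dose rule (11.0).** To be evaluable, "80% of the intended dose of all three drugs must be delivered in the first 2 cycles of chemotherapy".
- **Analysis set (14.1).** The primary pharmacodynamic sample "is expected to exclude patients who have incomplete data due to missed PET scans or due to study withdrawal for toxicity". There is no dose threshold, and multiple imputation is mentioned as a possibility.
- **Chemotherapy changes (7.7.3).** Treatment is held for Grade 3 or 4 toxicity. "Dose modifications for doxorubicin and ifosfamide-related toxicity will be based on" the investigator's discretion. Patients delayed by more than 3 weeks are taken off study.
- **Replacement (7.8).** Patients withdrawn before surgery are replaced.

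**The concern.** The run-in SUV change is fixed at the second PET. Doxorubicin and ifosfamide come later and cannot alter it. Even so, 7.8 makes that value's use depend on how much of those drugs the patient goes on to receive, and makes no exception for endpoints already measured. The run-in trough-SUV correlation is lost in the same way.

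A patient with both run-in scans whose chemotherapy is then cut has complete run-in data. Nothing in 14.1 clearly removes that patient, whereas 7.8 does. Two analysts following different sections would report different primary comparisons in a 21-patient trial, and the choice between them could be made after the data are seen.

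The two dose rules also differ from each other. Section 7.8 has no window. Section 11.0 counts the first two chemotherapy cycles for all three drugs, although the treatment plan in 7.0 gives no pazopanib in those cycles.

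**Working it through.** **1. Order of events.** The sequence is baseline PET, 14-day run-in with troughs, second PET and MRI, washout of at least 6 days, cycles 1 and 2, then third PET. The primary value in 14.1 uses only the first two PETs. The doxorubicin/ifosfamide criterion uses only what follows them.

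**2. Who fails the rule, using 11.0's two-cycle window.**
- Doxorubicin: 2 × 75 = 150 mg/m² intended; 0.8 × 150 = 120 mg/m² needed.
- Ifosfamide: 2 cycles × 5 days × 2 g/m² = 20 g/m² intended; 0.8 × 20 = 16 g/m² needed.
- Stopping after cycle 1: 1/2 = 50%, fails.
- A 25% cut in both cycles: 75%, fails.
- A 25% cut in cycle 2 only: (1 + 0.75)/2 = 87.5%, passes.
- After a full cycle 1, cycle 2 must fall below 60% of dose to fail, since (1 + 0.60)/2 = 80%.

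**3. The plan's own power figure.** Inputs from 14.2: SD 20, means 0 and −30, n = 21, 2:1 allocation (14 pazopanib, 7 placebo). Two-sided alpha of 0.05 is assumed because none is stated. By normal approximation, power = Φ(30/SE − 1.96) with SE = 20 × √(1/n₁ + 1/n₂).

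For 14 v 7: SE = 20 × √(1/14 + 1/7) = 9.26; 30/9.26 = 3.24; Φ(3.24 − 1.96) = 0.90. This reproduces the stated value of approximately 90%, with all 21 patients contributing.

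For the rank-sum test that 14.1 says will likely be used, simulated power with normal data and exact p-values is 0.83. The gap between 0.90 and 0.83 comes from the choice of test and approximation, not from the dose rule. Each column below should be compared only with its own first row.

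**4. Power after unreplaced exclusions.** The numbers lost are assumptions, since the documents give no rate. Exclusions are taken as unrelated to SUV change.

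| Pazopanib v placebo | Lost | Normal approximation | Exact rank-sum |
|---|---|---|---|
| 14 v 7 | 0 | 0.90 | 0.83 |
| 13 v 7 | 1 | 0.89 | 0.82 |
| 14 v 6 | 1 | 0.87 | 0.77 |
| 13 v 6 | 2 | 0.86 | 0.78 |
| 12 v 6 | 3 | 0.85 | 0.75 |

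For 13 v 6: SE = 20 × √(1/13 + 1/6) = 9.87; 30/9.87 = 3.04; Φ(3.04 − 1.96) = 0.86. Placebo losses cost most because that arm is small. The rank-sum column is not strictly monotone because the exact test is discrete at these sizes.

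**The case against.** **The rule has a legitimate target.** Sections 4.2.1 and 11.1 count SUV after two cycles as primary, and a patient who received little chemotherapy says little about that change. This stands. The fault is that the rule's scope is not limited, so it reaches endpoints that chemotherapy dosing cannot affect.

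**14.1 is the endpoint-specific statistical text and an analyst would follow it.** That is likely, but no text gives it precedence. Its wording is an expectation, whereas 7.8 is categorical. It would be too strong to say that 14.1 fixes a firm competing analysis set.

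**Replacement protects the sample size.** In part it does. Toxicity delays beyond 3 weeks take a patient off study, and withdrawal before surgery triggers replacement. Many patients who stop after cycle 1 would follow that path. Patients who stay on study below 80% are not clearly covered, and the loss mainly concerns them.

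**Under-dosing may be rare.** Cycle 1 would normally start at full dose, a failing cut in cycle 2 must exceed 40%, and growth factor is required after every cycle (7.4.2). This argues against assuming that a fifth or more of patients would be lost. The table therefore stops at 3 of 21.

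**The two dose rules can be read together.** Section 11.0 may supply the window that 7.8 lacks, with pazopanib counted over the run-in. That is a fair reading, but the text should say so.

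**Conclusion.** The point holds as a defect of scope. As written, 7.8 and 11.0 discard valid run-in data for reasons that arise after the endpoint is measured, and they do not agree with 14.1. The textual finding is firm. Its size is illustrative: on 14.2's figures, two unreplaced losses (13 v 6) cost about 4 points of power by normal approximation (90% to 86%) or about 5 points by exact rank-sum (83% to 78%). This rests on two-sided 0.05, normal SUV changes, and exclusions unrelated to SUV change. Such exclusions lose power but do not bias the comparison.

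A reader might infer a further bias: patients whose tumours progress at the run-in scan are stopped under 7.5, miss chemotherapy, and drop out of the comparison, mostly from placebo. The documents do not support this. Section 7.8 leaves room for investigator discretion on progression. The treatment plan ties only later cycles to imaging: "Cycles 3 and 4 will only be given if there is a response to chemotherapy identified on imaging after cycles 1 and 2". PERCIST progression on SUL peak also needs a rise of 0.8 units as well as more than 30% (11.3.1). Nothing requires every patient with a rise above 30% to be denied chemotherapy, so no bias should be claimed from this route.

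**What to change.** 1. In 7.8 and 11.0, limit the 80% doxorubicin/ifosfamide criterion to the post-chemotherapy SUV and response endpoints, and use one dose window (the first two cycles) in both sections.
2. In 14.1, state that every randomised, treated patient with a baseline and a post-run-in PET is in the primary run-in comparison, and in the run-in trough correlation where a trough was drawn, regardless of later chemotherapy.
3. Make any 80% condition on the run-in drug a sensitivity analysis.

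The cost is a text amendment to 7.8, 11.0 and 14.1. It adds no patients, scans or visits, and the post-chemotherapy endpoints keep their dose rule. Section 7.5 needs no change for this purpose.
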